**Safety Assessments:**

All clinical and laboratory adverse events will be graded according to the Common Terminology Criteria for Adverse Events v4.0 as outlined in Appendix 3. All patient reported adverse events will be evaluated. The most common reactions seen with dalbavancin to date are nausea, vomiting, diarrhea, headache, rash, and pruritis. For patients on study protocol following both intravenous and intraperitoneal dalbavancin administration, in the event of grade 2 or higher clinical or laboratory adverse events, these will be reported to the study physician, [name] or the study safety officer [name] within 24 hours and the need for and type of follow-up care will be determined by [name] or [name] (e.g., physician evaluation, follow-up labs, discontinuation of study medication, etc). Subjects will be discontinued from study for any grade 3 or 4 adverse events associated with dalbavancin administration.

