### IV. Research Methods

#### A. Outcome Measure(s):

The primary endpoints for the study are to (1) determine dalbavancin plasma pharmacokinetics in peritoneal dialysis patients after intravenous and intraperitoneal administration and (2) determine dalbavancin peritoneal fluid pharmacokinetics in peritoneal dialysis patients after intravenous and intraperitoneal administration.

Secondary endpoint is to evaluate patients for any adverse effects potentially associated with intraperitoneal administration of dalbavancin.

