**Washout:** During the 45 day or greater washout portion of this study the patients will not be asked to come in for any visits. This timeframe, which is greater than 5 half-lives of dalbavancin, is to ensure that all of the medication (dalbavancin) has left the patients' system before administering another dose of the medication.

**Laboratory tests:** The laboratory tests to be performed as part of this study include pregnancy testing to confirm eligibility and comprehensive metabolic panels if one is not documented within 30 days prior to the initiation of protocol to determine Child-Pugh score. These will be done at an initial screening visit if required to coincide with clinic appointment before visit 1.

**Pharmacokinetic Assessments:** 4 mL of blood will be collected in a purple top (EDTA) tube and 4 mL of peritoneal fluid in a urine collection cup at pre-dose, and 1, 2, 3, 4, 6, dialysis volume exchange. Blood and peritoneal fluid will be placed in an ice bath to chill until centrifuged. Plasma will be harvested within 30 minutes of each blood sample and will be stored at -80°C until assaying.

**Sample Coding and Storage:** Study samples will be coded with an indirect identifier and stored in [name] access-controlled laboratory.

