**Risks of Procedures:**

Side effects of dalbavancin include:

Most Common

- Nausea (5.5%)
- Vomiting (2.8%)
- Diarrhea (4.4%)
- Headache (2.7%)
- Rash (2.7%)
- Pruritus (2.1%)

Less Common (Less than 2% of patients)

- Anemia, hemorrhagic anemia, leucopenia, neutropenia, thrombocytopenia, petechiae, eosinophilia, thrombocytosis, gastrointestinal hemorrhage, melena, hematochezia, abdominal pain, infusion-related reactions, hepatotoxicity, anaphylactic reaction, *Clostridium difficile* colitis, oral candidiasis, vulvovaginal mycotic infection, hepatic transaminases increased, blood alkaline phosphatase increased, international normalized

ratio increased, blood lactate dehydrogenase increased, gammaglutamyl transferase increased, hypoglycemia, dizziness, bronchospasm, flushing, phlebitis, wound hemorrhage, spontaneous hematoma

It is not expected that patients will have all of these side effects. Other side effects may occur that were not seen before. Side effects are usually temporary and manageable. However, it is possible that these side effects could be serious or fatal.

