Appendix 1:

Appendix 2. Schedule of Events

	Blood Volume (mL)	Tube Type	Visit 1	Visit 2	Visit 3	Washout	Visit 4	Visit 5	Visit 6
Duration (days)			1	1	1	At least 45	1	1	1
Consent			x						
CMP	7	Green	x				x		
Urine pregnancy test			x				x		
Study drug administration			x				x		
Intensive Pharmacokinetic Sampling (4 mL for each drug in purple top tubes)	36	Purple	x				x		
Follow up Pharmacokinetic Sampling	4	Purple		x	x				
Clinical Adverse Events Assessed			x	x	x		x	x	x
Blood volume (mLs) b			43	4	4		43	4	4

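### Laboratory adverse events are to be graded and reported after both routes, but no laboratory safety test is scheduled on day 7 or day 14 after either dose.

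*Combined protocol and SAP*

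**What the plan says.** Section IV.D, Safety Assessments, makes two commitments on laboratory events. The first is on grading: "All clinical and laboratory adverse events will be graded according to the Common Terminology Criteria for Adverse Events v4.0". The second covers both routes: "in the event of grade 2 or higher clinical or laboratory adverse events, these will be reported to the study physician" or the safety officer within 24 hours. The response is then decided case by case ("e.g., physician evaluation, follow-up labs, discontinuation of study medication, etc"). The same paragraph takes a subject off study for a grade 3 or 4 event associated with dalbavancin.

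The Laboratory tests paragraph of IV.D describes what will be measured: "The laboratory tests to be performed as part of this study include pregnancy testing to confirm eligibility and comprehensive metabolic panels", the panel being needed only if none is on record within 30 days, to determine the Child-Pugh score. On timing it says: "These will be done at an initial screening visit if required to coincide with clinic appointment before visit 1". The Enrollment and Screening paragraph calls these safety labs but gives the panel the same Child-Pugh purpose.

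Appendix 2 marks the metabolic panel (CMP, 7 mL) at visits 1 and 4, the two dosing visits, and at no other visit. Its adverse-event row, marked at all six visits, is labelled "Clinical Adverse Events Assessed". Section IV.D gives visits 2, 3, 5 and 6 one blood and one peritoneal fluid sample each, and the washout has no visits.

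On the endpoint, section IV.A says: "Secondary endpoint is to evaluate patients for any adverse effects potentially associated with intraperitoneal administration of dalbavancin". The Risks of Procedures list includes "hepatic transaminases increased, blood alkaline phosphatase increased".

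**The concern.** The safety paragraph assumes laboratory results that the schedule does not collect. Patients do not usually notice a raised transaminase or alkaline phosphatase, so asking about symptoms on days 7 and 14 will not find one. If the plan is followed to the letter, the report could state that no laboratory adverse events occurred when no one had looked during the two weeks after dosing.

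This bears on Aim 3 and the secondary endpoint, both about adverse effects of intraperitoneal dosing, and on section G, which counts the side-effect profile among the knowledge to be gained. It also bears on the plan's own discontinuation rule. A silent laboratory event of grade 3 or 4 in the two weeks after dose 1 would not be seen when it occurred, so the rule cannot reliably act on it. That is an observation about the data available to the rule, not about the rule itself.

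**Working it through.** **Inputs.** Tube volumes and visit marks come from Appendix 2. The half-life of about 8.5 days is from section II. The washout of at least 45 days and the 10 patients, each dosed twice, are from section IV.C.

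**1. Is the missing panel real, or a broken table?** The volume row of Appendix 2 answers this.
- Visits 1 and 4: 36 mL pharmacokinetic + 7 mL panel = 43 mL. The table states 43.
- Visits 2, 3, 5 and 6: 4 mL pharmacokinetic + 0 mL panel = 4 mL. The table states 4.
- Total per patient: 2 × (43 + 4 + 4) = 102 mL.

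The totals leave no room for a panel tube at the four follow-up visits, and the visit description in IV.D agrees.

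**2. Scheduled panels on day 7 or 14.** There are none, for any of the 10 × 2 = 20 planned dosings.

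**3. Where the later panel falls.** Fraction of drug left = 0.5^(days/8.5), assuming simple mono-exponential decay.

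| Day after dose | Half-lives | Drug left | Panel scheduled? |
|---|---|---|---|
| 7 | 0.82 | 57% | No |
| 14 | 1.65 | 32% | No |
| 45 (washout counted from dose 1) | 5.3 | 2.5% | Visit 4, dose 1 only |
| 59 (washout counted from visit 3: 14 + 45) | 6.9 | 0.8% | Visit 4, dose 1 only |

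Appendix 2 places the washout after visit 3, which favours day 59; 45 days is the lower bound. After dose 2 there is no panel on any later day.

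**4. The two descriptions of the panel.** The Laboratory tests paragraph places it before visit 1, if required. Appendix 2 adds visit 4. On the paragraph alone, no panel follows either dose.

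**5. What ten patients could show if measured.**
- Chance of at least one event at a 2% rate: 1 − 0.98^10 = 18.3%.
- Exact two-sided 95% upper limit after 0 events in 10: 1 − 0.025^(1/10) = 30.8%.

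**The case against.** The strongest reply is that little would be gained. The plan lists these laboratory reactions among those seen in fewer than 2% of patients, and ten patients would probably show none. A clean set of panels would exclude only rates above about 31%. This is true, and it is why the point ranks below the primary pharmacokinetic aims. It does not remove the gap: a limit of 31% is weak, but without measurement there is no limit at all. The documents also give no laboratory event rates for the intraperitoneal route.

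A second reply is that the plan allows follow-up labs, evaluates patient-reported events and sees patients in routine clinic, so some results may exist. This stands in part. Symptomatic harm, or harm from dose 1 that persists to visit 4, could surface. But follow-up labs respond to an event already known, and the plan does not commit to reviewing routine-care results.

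Three stronger readings are tempting and should not be made.
- A reader might infer that laboratory harm cannot be detected at all. The routes just described rule that out; what is missing is scheduled, systematic assessment.
- A reader might infer that the comparison of routes is lopsided because only the first dose is followed by a panel. Order is randomised, so the imbalance is by period, not route. Moreover, section IV.F plans route comparisons of pharmacokinetics and pharmacodynamics only, not of safety.
- A reader might take the panels at visits 1 and 4 as drawn before dosing. Appendix 2 gives the visit but not the time. If drawn after dosing, they would still fall within a visit of about 8 hours and would say nothing about days 7 to 14.

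**Conclusion.** The concern holds as a mismatch between a safety commitment and the schedule meant to support it. The number of scheduled laboratory safety tests on day 7 or 14 is zero after both doses. At best there is one panel on a later day, at visit 4, 5.3 to 6.9 half-lives after dose 1. On the wording of the Laboratory tests paragraph there may be none. Silent laboratory changes cannot be systematically detected for either route, and a statement of laboratory safety would have no data behind it.

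The count of tests follows directly from the documents. The drug-remaining figures assume mono-exponential decay at the 8.5-day half-life quoted in section II; the half-life in patients on peritoneal dialysis is among the things the trial sets out to estimate. A change is advisable because it is cheap and supports a stated aim. It does not threaten the primary endpoints.

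**What to change.** Reconcile the Laboratory tests paragraph with Appendix 2 on whether a panel is drawn at visit 4. Then take one of two courses.

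**Measure.** Add the plan's own 7 mL metabolic panel tube to the existing draws at visits 2, 3, 5 and 6, or at minimum at visits 3 and 6 (day 14 of each period). State that the panels at visits 1 and 4 are drawn before dosing and serve as period baselines. Tabulate laboratory grades after each administration over days 0 to 14.
- Blood: 4 × 7 = 28 mL more per patient, from 102 to 130 mL; the minimum option adds 2 × 7 = 14 mL, giving 116 mL. Each follow-up visit with a panel goes from 4 to 11 mL.
- Other cost: a short amendment and two to four panels per patient, with no new visit. The documents give no price or staffing figures.
- Limit: a metabolic panel does not cover the blood counts or INR that also appear in the risk list, so the report should name what was measured.

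**Or narrow the claim.** Delete the word *laboratory* from the grading and reporting sentences of Safety Assessments, and limit the safety conclusion (Aim 3, section IV.A, section G) to clinical adverse events. The endpoint sentence itself does not use the word, so it needs a limit on interpretation, not a deletion. This costs wording only, but leaves laboratory safety of the intraperitoneal route unstudied.

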### **I. Hypotheses and Specific Aims:**

#### Hypothesis:

Dalbavancin maintains adequate plasma and peritoneal fluid concentrations for 2 weeks after a single 1500 mg dose when administered intravenously or intraperitoneally, making it a viable and convenient option for treating peritoneal dialysis patients with peritonitis

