#### C. Study Design and Research Methods

This study is an open label, cross-over study, evaluating the plasma and peritoneal fluid pharmacokinetics of dalbavancin after either intravenous or intraperitoneal administration. The

patients will be randomly assigned to receive dalbavancin either intravenously or intraperitoneally on study visit 1. The patients will receive the alternate administration technique following the washout period at visit 4. Patients will be administered dalbavancin either intravenously or intraperitoneally on study day 0. Pharmacokinetic analysis will be conducted on days 0, 7, and 14. Following the wash out period of 45 days or greater, the same 10 patients will cross-over and then be administered dalbavancin via the alternate administration technique received in visit 1 on study day 0. Pharmacokinetic analysis will be conducted again on days 0, 7, and 14. (see Appendix 1)

*Sample Size:*

Ten (n=10) patients will be evaluated in this pharmacokinetic evaluation. Since this is a descriptive pharmacokinetic study a sample size calculation was not performed

*Plasma and peritoneal fluid sampling:*

Dalbavancin will be administered on study day 0. On the intravenous administration day dalbavancin will be administered as a 30-minute IV infusion. On the intraperitoneal administration day, dalbavancin will be administered in the peritoneal dialysis fluid with a 6 hour dwell time. On day 0, patients will undergo plasma and peritoneal fluid pharmacokinetic sampling for determination of dalbavancin concentrations at time zero, 1 hour, 2 hours, 3 hours, 4 hours, 6 hours, at time of volume exchange. Patients will be given a specimen collection cup and asked to collect ~30 ml of peritoneal dialysate following scheduled nocturnal dwell approximately 24 hours following the administration of dalbavancin administration. Patients will report for a single PK measurement on study days 7 and 14. (18 total plasma and 18 total peritoneal fluid samples per patient). Blood samples will be drawn from a peripherally inserted intravenous catheter. Peritoneal fluid samples will be drawn from the already placed peritoneal dialysis catheter. Blood samples will be immediately centrifuged at 3000g and plasma and peritoneal fluid samples will be stored at -80°C until analysis.

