**D. Description, Risks and Justification of Procedures and Data Collection Tools:**

**Enrollment and Screening:** Study subjects will be contacted an enrolled through [name] clinic. Initial contact will be made by phone prior to a clinic appointment to discuss initial interest of the patient. Further information and enrollment will take place at a clinic visit or time of the patients choosing. Enrollment will take place in a private room at [name] clinic. Initial baseline and demographic information will be gathered for enrolled patients at the time of enrollment. Safety labs (comprehensive metabolic panel and urine pregnancy test for women of childbearing potential) will be drawn or performed at [name] clinic and will coincide with a scheduled clinic visit closest to study protocol initiation. The comprehensive metabolic panel will be drawn to evaluate Child-Pugh score if there is no comprehensive metabolic panel within the medical record within 30 days of protocol initiation.

**Visit 1 and 4:** (~8 hours): On visits 1 and 4 the patients will undergo intensive PK sampling. Inclusion and exclusion criteria will be reviewed with the patient at each visit prior to initiation of the protocol. Subjects will be admitted to the CTRC in the morning and a "saline-lock" will be placed. The dalbavancin preparations will be prepared and managed by [name] or [name] who are both clinical pharmacists with training in sterile drug preparation. The dalbavancin 1500 mg will either be administered, by CTRC nursing staff, intravenously (as randomly assigned) or into the intraperitoneal space (as randomly assigned) using the patient's existing peritoneal dialysis catheter with the patients currently prescribed dialysate. Following the blood and peritoneal fluid collection at the second dialysis volume exchange, the subjects will be discharged and asked to return at a scheduled time on day 7. Patients will also be given a specimen collection up with instructions to collect approximately 30 ml of peritoneal dialysate following their evening nocturnal dwell. The collected dialysate will be returned to the investigators.

**Visit 2, 3, 5, and 6:** (~60 minutes): A "saline-lock" will be placed and a single blood and peritoneal fluid sample will be collected at each of these visits. All blood and peritoneal fluid draws will be

completed at the outpatient CTTC. The patient will be discharged and follow up visits will be scheduled for day 14 or next intensive PK sampling visit.

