Pharmacodynamic parameters will be evaluated in order to determine whether dalbavancin dosing results in initial and steady-state plasma and peritoneal concentrations that are adequate for treatment of infections due to common pathogens (Staph aureus, Coag neg staph, and enterococcus). Monte Carlo simulation (Crystal Ball version 7, Decisioneering, Inc., Denver, CO) will be used in this study to calculate probability of target attainment (PTA) for pharmacodynamic goals. The model randomly applies values for  $C_{max}$  and  $AUC_{0-12}$  derived from data obtained from the study patients. We will utilize CLSI and EUCAST MIC data for the common gram positive pathogens. We will place these MIC distributions into our Monte Carlo simulation for comparison to dalbavancin plasma concentrations and PK variability. From these studies, MIC frequency distributions will be constructed and used in the Monte Carlo simulations. Ten thousand simulations will be performed at each MIC value and for each of the selected pathogens.

[figure not shown]
[figure not shown]
*Statistical comparisons of PK/PD findings*

Intra-patient pharmacokinetics and pharmacodynamics of dalbavancin will be compared between intravenous and intraperitoneal administration using the paired-t test. Given the sample size of 10 patients completing each phase of the study, we will be able to detect a mean difference in area under the curve between the two treatment modalities of 1527 mg·hr/L at a power of 80%. Probability of target attainment will be compared with the paired t-test. Statistical comparisons will be compared using SAS version 9.3. A p-value < 0.05 will be considered significant.

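### A dalbavancin-associated grade 3 or 4 event takes the patient out of the study, not only off further drug, so the late samples and scheduled safety assessments of a dose already given are lost (minor, cheap to fix)

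*Combined protocol and SAP*

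**What the plan says.** Section IV.D, Safety Assessments, has two consecutive provisions.

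- Events of grade 2 or higher are reported to the study physician or safety officer within 24 hours, and "the need for and type of follow-up care will be determined by" one of them. The examples given are "physician evaluation, follow-up labs, discontinuation of study medication".
- The next sentence is mandatory: "Subjects will be discontinued from study for any grade 3 or 4 adverse events associated with dalbavancin administration".

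The schedule that this rule cuts short is in Section IV.C: "Patients will report for a single PK measurement on study days 7 and 14", giving "18 total plasma and 18 total peritoneal fluid samples per patient". Section IV.D says that after each dosing visit "the subjects will be discharged and asked to return at a scheduled time on day 7". Appendix 2 schedules a clinical adverse-event assessment at all six visits.

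The hypothesis in Section I is that "Dalbavancin maintains adequate plasma and peritoneal fluid concentrations for 2 weeks after a single 1500 mg dose". Section IV.A makes plasma and peritoneal pharmacokinetics the primary endpoints and adverse effects of the intraperitoneal route the secondary endpoint.

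**The concern.** The protocol treats stopping the drug and leaving the study as different actions, because it names the first as an option and then mandates the second. No text keeps a discontinued patient in day 7 and 14 sampling or in the scheduled assessments, and there is no early-termination visit.

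In a single-dose design this has a particular effect:

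- **First-period event.** Withholding the visit 4 dose is right. Dropping visits 2 and 3 adds no protection from the drug, because that dose has already been given.
- **Second-period event.** No study drug remains, so removal prevents no exposure. Visits 5 and 6 are lost.

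At stake are the late samples, which are the only direct evidence on the two-week claim, and the scheduled safety observations in exactly the patients who reacted badly. At the 8.5-day half-life in Section II and simple one-phase decay, about 57% of drug remains at day 7 (2^(−7/8.5)) and 32% at day 14 (2^(−14/8.5)). Scheduled assessment could therefore end while exposure is still substantial.

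**Working it through.** **1. What is sampled.** Section IV.C gives 18 plasma samples over two periods, or 9 per period: seven on day 0 (time zero, 1, 2, 3, 4 and 6 h, and the volume exchange), then one each on days 7 and 14. I place the exchange sample at 8 h, from the stated visit length of about 8 hours. The home dialysate sample at about 24 h is not a plasma sample.

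**2. Elimination constant under one-phase decay.** k = ln 2/(8.5 × 24) = 0.0034 per hour. For a log-linear fit, SE(k)/k = (CV/√Sxx)/k, with an assumed concentration error (CV) of 5, 10 or 15%. The pre-dose sample does not enter.

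| Samples used | Sxx (h²) | SE(k)/k at CV 5, 10, 15% |
|---|---|---|
| 1, 2, 3, 4, 6, 8 h | 34 | 2.5, 5.0, 7.6 |
| plus day 7 | 23,088 | 0.10, 0.19, 0.29 |
| plus days 7 and 14 | 106,402 | 0.05, 0.09, 0.14 |
| days 7 and 14 only | 14,112 | 0.12, 0.25, 0.37 |

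With day 0 alone the standard error is 2.5 to 7.6 times the quantity itself, so no individual estimate is usable. AUC0-∞ fails with it, because 2^(−8/204) = 97% of that area lies after 8 h. A distribution phase would lower this share somewhat.

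The last row matters because Section IV.F plans one-, two- and three-compartment models. If the day 0 samples are not on the terminal phase, the full schedule gives 12–37% error, and a patient with day 7 but not day 14 has a single terminal point and no individual slope.

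These figures are for plasma. The late peritoneal samples are lost too, but I have not quantified that loss.

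**3. What survives.** Cmax, Tmax, the fraction of the intraperitoneal dose absorbed and the 0–6 h peritoneal rate constant come from day 0. Plasma falls only 1 − 2^(−4/204) = 1.35% from 8 to 12 h; holding the 8 h value flat changes AUC0–12 by 0.2%. In the Monte Carlo analysis, "The model randomly applies values for" Cmax and AUC0–12, so target attainment is largely unaffected. The mixed-effects model could also use a partial profile.

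**4. How often the fix would help.** The documents give no grade 3–4 rate. Assume p = 1% or 2% per dose, and a fraction f = 25%, 50% or 100% of such events before day 7. A first-period event ends dosing, so with 10 patients:

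- P(at least one single-dose profile saved) = 1 − [1 − pf − (1 − p)pf]^10
- P(at least one IV–IP pair saved; second-period events only) = 1 − [1 − p(1 − p)f]^10

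| p | Profile, f = 25, 50, 100% | Pair, f = 25, 50, 100% |
|---|---|---|
| 1% | 5, 10, 18% | 2, 5, 9% |
| 2% | 9, 18, 33% | 5, 9, 18% |

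These are upper bounds, because they assume that every affected patient continues. If half do (an assumption), the ranges become 2–18% for profiles and 1–9% for pairs.

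**5. Power.** Section IV.F states a detectable AUC difference of 1527 mg·hr/L at 80% power with 10 patients. It gives no standard deviation, so the figure cannot be reproduced independently. Back-solving a two-sided 5% paired t-test (sidedness assumed) gives a standard deviation of differences of 1533. At that value power is 80.0% with 10 pairs and 74.5% with 9, so one pair is worth about 5.5 points. Expected pairs saved are 10p(1 − p)f = 0.025 to 0.196, an average gain of 0.1 to 1.1 points, or half that if half continue.

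**The case against.** The strongest case is that this is a protective choice. Participants are uninfected volunteers with nothing to gain from sampling, and each follow-up visit means a new line, a blood draw and a catheter sample. Appendix 3 defines grade 3 partly by hospitalization or disability and grade 4 as life-threatening. Ending research procedures at that point is defensible, and many such patients could not or would not return. This stands as a limit on the benefit, which is why step 4 gives upper bounds and why the fix depends on agreement and clinical judgement. It does not justify removing a patient who is fit and willing.

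It can also be said that the rule never states that sampling stops, that staff may continue it, and that terms for continued participation may sit in the consent pages, which are not in the copy reviewed. That is possible. The point concerns only the Safety Assessments sentence, and continued sampling would depart from its plain meaning.

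The power argument is weak, and this is conceded: Section IV.C calls the study descriptive and says that no sample size calculation was done.

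A reader might infer that safety follow-up of the event itself ends. The text does not support that: the event is graded, reported within 24 hours and followed as the physician or safety officer decides. What that provision does not mention is PK samples or scheduled assessments.

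**Conclusion.** The point holds as a minor one. The rule as written discards late plasma and peritoneal data and scheduled safety observations for a dose already given, and after a second-period event it does so without sparing any drug exposure.

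For removal before day 7, the individual elimination constant, half-life, AUC0-∞ and systemic clearance for that dose are lost. For removal between days 7 and 14, a reader might take from the one-phase figures that the elimination constant stays usable with about twice the error. The planned multi-compartment modelling does not support that reassurance: the estimate is much less certain and may not be obtainable at all.

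Nor do the documents support reading this as a threat to a primary result. At an assumed 1–2% event rate per dose, the chance that the fix saves at least one profile is at most 5–33%. The average power gain is at most about 1 point, and only if the compared area is AUC0-∞ and withdrawn patients are not replaced; the plan states neither. The conclusion rests on the wording of the rule and the single-dose design, not on these figures.

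**What to change.** Replace the discontinuation sentence in Safety Assessments with:

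*Subjects with a grade 3 or 4 adverse event associated with dalbavancin will receive no further study drug; with the subject's agreement and if clinically appropriate, the remaining day 7 and 14 PK samples and adverse-event assessments for the dose already given will continue, and these data will be included in the analysis.*

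The clinical criterion for stopping drug is unchanged. The cost is one sentence; the visits are already scheduled, at about 60 minutes each with one blood and one peritoneal fluid sample. The downside is continued research sampling in a patient who has had a severe event, limited by consent and physician judgement.

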#### Specific Aims:

1. Determine dalbavancin plasma pharmacokinetics in peritoneal dialysis patients after intravenous and intraperitoneal administration
2. Determine dalbavancin peritoneal fluid pharmacokinetics in peritoneal dialysis patients after intravenous and intraperitoneal administration
3. Evaluate patients for any adverse effects potentially associated with intraperitoneal administration of dalbavancin

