Appendix 3: Adverse drug reaction grading

	Description
Grade 1	Mild ; asymptomatic or mild symptoms; clinical or diagnostic observations only; intervention not indicated
Grade 2	Moderate; minimal, local or noninvasive intervention indicated; limiting age-appropriate instrumental ADL
Grade 3	Sever or medically significant but not immediately life-threatening; hospitalization or prolongation of hospitalization indicated; disabling; limiting self-care ADL
Grade 4	Life-threatening consequences; urgent intervention indicated
Grade 5	Death related to adverse event
Complete description of grading for each system organ class can be found through the U.S. Department of Health and Human Services, National Institutes of Health, and National Cancer Institute at the following web address. https://ctep.cancer.gov/protocoldevelopment/electronic_applications/ctc.htm#ctc_40	

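### The required toxicity actions reach only the affected patient; after a severe intraperitoneal event, nothing obliges a review before other patients receive their intraperitoneal dose

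*Combined protocol and SAP*

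**What the plan says.** Two rules in section IV.D, Safety Assessments, require action on toxicity.

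- **Reporting.** After either route, an event of grade 2 or above goes within 24 hours to the study physician or the safety officer. The plan says that "the need for and type of follow-up care will be determined by" one of these two roles, and gives examples: "e.g., physician evaluation, follow-up labs, discontinuation of study medication, etc".
- **Discontinuation.** "Subjects will be discontinued from study for any grade 3 or 4 adverse events associated with dalbavancin administration".

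The only other check before dosing is in the Visit 1 and 4 paragraph of the same section: "Inclusion and exclusion criteria will be reviewed with the patient at each visit prior to initiation of the protocol". It concerns that patient's own eligibility.

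On design, section IV.C says: "The patients will receive the alternate administration technique following the washout period at visit 4". Each of the ten patients is therefore planned to have one intravenous (IV) dose and one IP dose. During the washout of at least 45 days, "the patients will not be asked to come in for any visits". The third specific aim is: "Evaluate patients for any adverse effects potentially associated with intraperitoneal administration of dalbavancin".

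**The concern.** A discontinuation rule protects patients by preventing further exposure to whatever caused the harm. Here it does so only in part. It spares an IP-first patient the later IV dose, and it spares an IV-first patient the IP dose after an event on IV. After an event on IP, the affected patient has no second IP dose to be spared. The people who could still be protected from the IP route are the patients not yet dosed that way, and neither rule mentions them.

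This matters because the participants do not have peritonitis and finding IP adverse effects is a stated aim. The side-effect percentages under Risks of Procedures are not given by route or grade, and that section warns of effects not previously seen. If the plan is followed to the letter, IP dosing of other patients continues after a severe related IP event unless someone chooses to intervene.

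**Working it through.** **Textual check.** The reporting rule ends in a decision about follow-up care, and its examples read naturally as care of the patient concerned. The discontinuation rule removes that patient. The pre-dose check is of the patient's own eligibility. Sections IV.C and IV.D and the Schedule of Events contain no hold, staggering, sentinel patient, cohort review or study stopping rule. So no text requires a review before another patient's IP dose.

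**Inputs for size.** From the plan: 10 patients with one IP dose each. The plan has no stopping boundary or IP event rate to reproduce. Assumed: the rate *p* of related grade 3 or higher events per IP dose is 1%, 2%, 5%, 10% or 20%; events are independent; all ten IP doses would otherwise be given; every hold becomes a stop. The dosing order is not stated, so two schedules are shown.

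**Formulas.**

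- Expected events with no hold: 10*p*.
- Probability that a hold is triggered: 1 − (1−*p*)^10.
- *Block schedule*: five IP-first patients are all dosed before the five IV-first patients get IP. IP doses lost = 5[1 − (1−*p*)^5].
- *Sequential schedule*: one patient at a time, each event known before the next IP dose. IP doses lost = 10 − [1 − (1−*p*)^10]/*p*.
- Events avoided = *p* × IP doses lost.

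**Example at p = 10%.** Triggered: 1 − 0.9^10 = 1 − 0.349 = 0.651. Block: 1 − 0.9^5 = 1 − 0.590 = 0.410; doses lost 5 × 0.410 = 2.05; events avoided 0.10 × 2.05 = 0.205. Sequential: doses given 0.651/0.10 = 6.51; doses lost 3.49; events avoided 0.10 × 3.49 = 0.349.

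| Assumed rate per IP dose | 1% | 2% | 5% | 10% | 20% |
|---|---|---|---|---|---|
| Expected events, no hold | 0.1 | 0.2 | 0.5 | 1.0 | 2.0 |
| Hold triggered | 10% | 18% | 40% | 65% | 89% |
| Events avoided, block | 0.002 | 0.01 | 0.06 | 0.20 | 0.67 |
| Events avoided, sequential | 0.004 | 0.02 | 0.10 | 0.35 | 1.11 |
| IP doses lost of 10, block | 0.2 | 0.5 | 1.1 | 2.0 | 3.4 |
| IP doses lost of 10, sequential | 0.4 | 0.9 | 2.0 | 3.5 | 5.5 |

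**Sensitivity.** The plan states random assignment but no balance. Under the block schedule with 3 to 7 IP-first patients, events avoided at 5%, 10% and 20% are 0.05–0.06, 0.16–0.21 and 0.47–0.71; with 0 or 10 IP-first patients the figure is nil. If only half of the holds become stops, the 5/5 block figures halve to 0.03, 0.10 and 0.34.

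**What the plan leaves unreviewed.** Under sequential dosing, once a first event occurs, the mean number of later IP doses with no required review is 4.9, 5.4 and 6.2 at 5%, 10% and 20% (for example 1.97/0.401 = 4.9).

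**The case against.** The strongest reply is that this is an optional safeguard. Nothing in the plan is contradictory or miscalculated. The study is small and open-label, with one dose per period. The Background describes 1500 mg as safe and effective, and reports that guidelines favour IP antibiotics for peritonitis. There is a safety officer, reporting within 24 hours from grade 2, and an open-ended list of actions. What remains is the difference between may and must. That is fair and it limits the priority. It does not supply the missing requirement.

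Three stronger readings are tempting, and the documents do not support them.

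- *Nobody can stop IP dosing.* The officer is free to intervene, and nothing obliges dosing to go on.
- *Deaths fall through a gap.* Appendix 3 defines grade 5 as "Death related to adverse event", and the discontinuation rule names only grades 3 and 4. But a patient who has died cannot be discontinued, and the reporting rule already covers grade 5.
- *The IP route is shown to be hazardous.* The documents give no IP event rate. At 1–2% the benefit of a hold is close to nil.

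Two practical objections also stand. Because reports go to the physician or the safety officer, a compliant report might never reach the officer; the fix has to route it. And a hold triggered by any related event will sometimes respond to a known drug effect, such as a rash, rather than to the route. The officer can then release it.

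**Conclusion.** The point holds as a cheap safety improvement of low to moderate priority. The mandatory actions concern only the affected patient, and after an IP event they prevent no further IP exposure. Action on other patients is permitted but not required.

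Its size cannot be estimated from the documents. Over the assumed rates of 1% to 20%, events avoided run from about 0.002 to 0.67 under block dosing and from 0.004 to 1.11 under sequential dosing, if every hold becomes a stop. The pharmacokinetic results are unaffected unless a hold becomes a stop.

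The opening pages and the Appendix 1 figure are missing from the available text, and a separate monitoring plan may exist. If it already contains such a hold, a cross-reference in Safety Assessments would be enough.

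**What to change.** Add to section IV.D, Safety Assessments:

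> *Any grade 3 or higher adverse event associated with dalbavancin, with onset after an IP dose and before that subject's next study dose (or by the end of that period's follow-up), will be reported to the study safety officer within 24 hours and places further IP dosing of all subjects on hold until the safety officer records a decision to continue, modify or stop.*

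For IP-first patients the window closes at the visit 4 IV dose, so an event on IV cannot trigger an IP hold. For IV-first patients it closes at visit 6 (day 14).

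The cost is a one-sentence amendment using the existing officer and reporting interval, with no new committee and no staggering. The downsides are a review pause, at the trigger frequencies tabulated above, and fewer IV/IP pairs for the paired comparison if a hold becomes a stop: on average 1.1, 2.0 and 3.4 of 10 (block) or 2.0, 3.5 and 5.5 (sequential) at 5%, 10% and 20%. A hold lifted after review costs only time.

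The hold cannot protect patients dosed before the event is known. With no washout visits, an event starting then surfaces only when the patient reports it or at visit 4.
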